The most effective and durable treatment for both obesity and type 2 diabetes mellitus (T2DM) remains bariatric surgery. Alternative surgical techniques have been sought to improve the rates of T2DM remission. Standard Limb RYGB and biliopancreatic diversion (BPD) has been showed to lead to a matched total body weight loss of 33% at 2 years post-operatively. Unfortunately, the BPD procedure has the distinct disadvantage of a substantially higher risk of developing severe nutritional complications, and this has limited its use.

To improve the glucose-lowering efficacy of Standard Limb RYGB, whilst avoiding the high risk of complications with the BPD procedure, the Long Limb RYGB has been devised as a hybrid operation that combines the standard design of Standard Limb RYGB, but with a longer biliopancreatic limb. Previous research has suggested that the rates of any complications, including nutritional, were not higher than those reported after Standard Limb RYGB.

The main anatomical difference between Long Limb RYGB and Standard Limb RYGB is that the segment of the bypassed proximal intestine, the biliopancreatic limb, is longer (150 vs. 50cm respectively). This means that in the Long Limb RYGB the common channel is shorter, and as a result nutrients reach the distal small bowel faster and in a less-digested state. The hypothesis is that the Long Limb RYGB is better for treatment of T2DM because: a) It increases post-prandial secretion of gut hormones, and in particular glucagon-like peptide-1 (GLP-1) which results in the immediate post-prandial insulin secretion significantly higher than the Standard Limb RYGB.

b) It increases insulin sensitivity significantly more than the Standard Limb RYGB, before and after weight loss has taken place.

The trial will evaluate the efficacy on T2DM of the Long Limb RYGB compared to the Standard Limb RYGB, and investigate the mechanisms underlying any potential differences by conducting:

- 1. Mechanistic assessments with Mixed Meal Tolerance Test (MMTT) and Hyperinsulinaemic Euglycaemic Clamp at: pre-operative, early mechanistic postoperative (at 1-2 weeks after the surgery) and late mechanistic post-operative visits (at 20% total body weight loss after the surgery).
- 2. Clinical assessment pre-operatively, at the day of surgery and at 3, 6 and 12 months post-operatively.

4 Study Methods

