6.3.2 Secondary outcome measures

The secondary endpoints are measured at several different timepoints.

Endpoints from mixed meal test at late mechanistic post-operative visit:

• Peak of active GLP-1 concentration

Endpoints from both early and late mechanistic post-operative visits:

- a) From the Hyperinsulinaemic Euglycaemic Clamp
 - Rate of glucose appearance (Ra) and disposal (Rd) and metabolic clearance rate of glucose (MCR) basal, low and high
- b) From the MMTT:
 - Active GLP-1 concentration (AUC)
 - Total GLP-1 (peak, AUC)
 - PYY (peak, AUC)
 - GIP (peak, AUC)
 - Markers of insulin secretion (peak, AUC)
 - Plasma glucose (peak, AUC)
 - Bile acids (peak, AUC)
 - FGF-19 and 21 (peak, AUC)
 - Systolic and diastolic blood pressure (AUC)
 - Heart rate (AUC)
 - Appetite ratings (Visual Analogue Scales; AUC)
- c) Blood, urine and faecal microbial diversity and metabolomics
- d) Total caloric intake and macronutrient composition % fat, % protein, % carbohydrates
- e) Body composition and Basic Metabolic Rate (BMR)

Endpoints at the day of surgery:

- Common channel length
- Total small bowel length
- Proportion of common channel to total small bowel length
- Operating time
- Length of in hospital stay

Endpoints at 3, 6 and 12 months:

- HbA1c
- % of total body weight loss
- Number of glucose lowering medications

Secondary endpoints at 12 months:

- % of total body weight loss
- BMI
- Body composition
- Basic Metabolic Rate (BMR)
- Waist, hips and neck measurements
- T2DM remission
- Comorbidities
- Medications
- King's Obesity Staging Score
- Systolic and diastolic blood pressure
- Heart rate
- Oxygen saturation
- Bowel movements frequency

- Blood tests: fasting plasma lipids concentration, fasting plasma glucose, haematinics, vitamins
- Total caloric intake
- Macronutrient composition % fat, % protein, % carbohydrates
- Faecal caloric content

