6.3.3 Safety outcomes

Safety will be assessed by the recording of adverse events (AEs) and serious adverse events (SAEs) reported during the operation for up to one-year following surgery. This will include medical, surgical, nutritional and psychological complications adverse events.

An SAE will be defined as an adverse event that meets any of the follow criteria:

- Leading to death
- Life-threatening
- Leads to hospitalisation or prolongation of existing hospitalisation
- Persistent or significant disability or incapacity
- Congenital anomaly or birth defect.

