9.4 Other Analyses

An additional set of analyses will examine the association between the key primary and secondary efficacy outcomes measured on a continuous scale and the proportion of the common channel length to the total small bowel length. The analysis will be performed using Pearson correlation. Alternatively, Spearman's rank correlation will be used if the Pearson correlation assumptions (e.g. non-linear relationship, both variables non-normally distributed) are not met. For each outcome, a single analysis will be performed for all patients, combining the two study arms together.

10 Safety Analyses

The main safety outcome is the occurrence of adverse events (AEs). For each of the study groups, the number of adverse events in each group and per patient will be summarised. Specific details of the adverse events will be recorded in addition to the number of AEs that are serious and non-serious.

If it is deemed that there are sufficient occurrences of adverse events in total, a formal test of significance will be performed to compare AE occurrence at the patient level between study arms. Fisher's exact test will be used for this analysis. However, it is acknowledged that the study is unlikely to be powered to show a difference between groups for this endpoint.

11 Technical Details

The data analysis will be primary performed using the statistical software packages Stata (version 15.1), SPSS (version 20 or later), GraphPad PRISM (version 6 or later). Programs recording details of all data manipulation and data analyses will be produced and kept, so that the analyses can be externally inspected and, if necessary, re-run.

The exception is for the analysis of the blood, urine and faecal microbial diversity and metabolomics outcomes, which will be analysed using the Vegan library within the R statistical package and the Statistical Analysis of Metagenomic Profiles software package.

12 Summary of Changes to the Analysis Plan

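### The only formal safety comparison pools all adverse events under a discretionary trigger; no between-arm comparison of nutritional complications is prespecified

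*SAP*

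**What the plan says.** - **Rationale (SAP introduction).** Biliopancreatic diversion (BPD) is described as carrying a "substantially higher risk of developing severe nutritional complications", which has limited its use. Long Limb RYGB is presented as a hybrid meant to gain glucose-lowering efficacy without that risk. Earlier research is said to suggest that complications, nutritional ones included, are no more frequent than after Standard Limb RYGB.
- **Objective (Section 6.1).** Comparing the safety of the two operations is among the secondary objectives.
- **What is collected (Section 6.3.3).** AEs and serious AEs are recorded for up to a year after surgery: "This will include medical, surgical, nutritional and psychological complications adverse events".
- **What is analysed (Section 10).** For each arm "the number of adverse events in each group and per patient will be summarised", details of events are recorded, and events are split into serious and non-serious. The four classes of 6.3.3 do not reappear. The formal comparison has a condition, "If it is deemed that there are sufficient occurrences of adverse events in total", with no threshold. If it is met, "a formal test of significance will be performed to compare AE occurrence at the patient level between study arms", and "Fisher's exact test will be used for this analysis". The section concedes that power for this endpoint is probably inadequate.
- **Laboratory nutrition data (Sections 6.3.2 and 9.2).** The 12-month secondary endpoints include "Blood tests: fasting plasma lipids concentration, fasting plasma glucose, haematinics, vitamins". On a continuous scale these are compared by baseline-adjusted ANCOVA, or by t-test or Mann-Whitney test where there is no baseline.

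**The concern.** The introduction singles out one kind of harm, and Section 6.3.3 arranges to record it. Section 10 then folds it into a single indicator of whether a patient had any AE. If other events are common, most patients count as having an event whatever happens nutritionally, and the indicator moves little between arms.

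The trigger adds to this. It depends on the total AE count, so the test is most likely to run when AEs are frequent, which is when the pooled indicator is least sensitive to a difference in one class. With no threshold set, the decision to test can also be made after the counts are known.

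At stake is how the trial's safety result is read. A null any-AE test could be taken to support the premise that the longer bypassed limb brings no extra nutritional complications, when the test had little chance of showing otherwise. Section 10 plans no effect estimate with an interval that would show the reader how much excess remains possible.

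**Working it through.** The SAP gives no power figure for the safety test, so there is none to reproduce.

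**Inputs from the SAP.** 1:1 allocation (Section 4.3); 25 patients per arm planned, 20 per arm required before the 20% dropout allowance (Section 5); Fisher's exact test at patient level (Section 10).

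**Assumptions, none from the SAP.** Two-sided test at 5%. Nutritional risk p_S = 8% in the Standard arm and p_L = 40% (large excess) or 24% (threefold excess) in the Long arm. Other AEs affect a proportion q of patients, equal in both arms and independent of nutritional events; q is varied from 20% to 90%.

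**Step 1: what pooling does to the difference.** The any-AE risk in an arm is 1 − (1 − q)(1 − p). The between-arm difference is therefore (1 − q)(p_L − p_S): the nutritional difference shrunk by the factor (1 − q). For 8% vs 40% and q = 60%:

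- Standard: 1 − 0.40 × 0.92 = 0.632
- Long: 1 − 0.40 × 0.60 = 0.760
- Difference: 0.128, that is 0.40 × 0.32

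**Step 2: exact Fisher power at 25 per arm**, summing the two binomial distributions over all tables with p ≤ 0.05.

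| Endpoint | 8% vs 40%: risks compared | Power | 8% vs 24%: risks compared | Power |
|---|---|---|---|---|
| Nutritional only | 0.080 vs 0.400 | 0.68 | 0.080 vs 0.240 | 0.22 |
| Any AE, q = 20% | 0.264 vs 0.520 | 0.38 | 0.264 vs 0.392 | 0.10 |
| Any AE, q = 40% | 0.448 vs 0.640 | 0.22 | 0.448 vs 0.544 | 0.08 |
| Any AE, q = 60% | 0.632 vs 0.760 | 0.10 | 0.632 vs 0.696 | 0.04 |
| Any AE, q = 80% | 0.816 vs 0.880 | 0.04 | 0.816 vs 0.848 | 0.03 |
| Any AE, q = 90% | 0.908 vs 0.940 | <0.01 | 0.908 vs 0.924 | <0.01 |

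A second pair of risks, 5% vs 30%, shows the same pattern: 0.55 for nutritional events alone, then 0.14, 0.07 and 0.04 at q = 40%, 60% and 80%.

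**Step 3: what a split by class can and cannot do.** At 25 per arm a nutritional-only Fisher test needs at least 6 patients against 0, or 7 against 1, to reach p ≤ 0.05. At 20 per arm its power for 8% vs 40% falls from 0.68 to 0.58. The split removes the dilution; it does not remove the limit set by the sample size.

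**Step 4: what an interval would show.** Newcombe 95% CIs for the risk difference, Long minus Standard, at 25 per arm:

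- 10/25 vs 2/25: 32 percentage points, CI 8 to 52.
- 2/25 vs 2/25: 0 points, CI −18 to +18.

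In the second case the p-value signals nothing, yet an excess of up to 18 points remains compatible with the data. The interval makes that visible.

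**The case against.** The strongest reply is that the data are not lost. Section 10 records event details and counts by arm, haematinics and vitamins are compared between arms at 12 months, and low power is openly conceded. All of this stands. A reader might infer from the pooled test that nutritional harm is hidden or cannot be assessed at all; the SAP does not support that reading. What the reply leaves open is that recording details is not a prespecified comparison, that a difference in average vitamin level does not show how many patients became deficient, and that the power concession concerns the any-AE endpoint and calls for no estimate.

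Second, the size of the dilution depends on AE rates that the SAP does not give. A reader might infer that nearly every patient will have an AE, so that the test must sit at its ceiling; that is unsupported. The range in the table answers this: at q = 20% power is already cut by almost half or more, but the near-zero values need a high background rate.

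Third, a nutritional-only test would itself miss a threefold excess most of the time (power 0.22). This stands in full, so the recommendation is estimation, not a different significance test.

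Fourth, the high nutritional risk quoted in the introduction belongs to BPD, which is not a trial arm, and the SAP sets no nutritional hypothesis. That is correct. It limits the point to a mismatch between the stated rationale and the planned safety output; it does not make it a failed hypothesis.

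**Conclusion.** The point holds as a gap in what Section 10 prespecifies. Its one formal comparison pools all AEs, its trigger has no threshold, and the nutritional class named in Section 6.3.3 gets no between-arm summary or estimate.

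Pooling weakens a nutritional signal at every background rate examined: from 0.68 to between 0.38 and under 0.01 for 8% vs 40%, and from 0.22 to between 0.10 and under 0.01 for 8% vs 24%. These figures rest on assumed rates, independence and equal background AEs, 25 patients per arm, and a two-sided 5% test.

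It would go too far to say that the harm cannot be assessed, or that splitting the test would make the trial adequately powered for it. The gain is a prespecified estimate and protection against misreading a null. This is a worthwhile, inexpensive improvement; it does not touch the primary analysis.

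**What to change.** In Section 10:

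1. Replace the conditional any-AE test with an unconditional table for each class in Section 6.3.3, nutritional first: patients with at least one event per arm, and the risk difference (Long minus Standard) with a 95% CI. Label it as estimation, with no significance claim, so that four classes raise no multiplicity question. Keep the serious/non-serious split.
2. State that the nutritional result will be read together with the 12-month haematinics and vitamins. Optionally add the proportion of patients per arm with a value below the laboratory's lower limit.
3. Extend the existing power caveat to say that a non-significant or near-zero difference will not be taken as evidence that complications are no more frequent after Long Limb RYGB.

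The cost is SAP wording and a few two-by-two tables on data already planned for collection. The downside is several wide intervals and no single safety p-value.

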12.1 Changes from Version 1.0 to 1.1

The following changes were made between the SAP versions:

- Reformatting of the order the sections
- Omission of demographic summaries for both study groups combined
- Addition of further secondary outcomes
- Details of LOCF approach to be used for MMTT data

12.2 Changes from Version 1.1 to 1.2

The following changes were made between the SAP versions:

- Change of approach for secondary outcomes from the MMTT to consider all measurements in the analysis, and not summary measures (peak, AUC).
- Change of statistical methods for secondary analysis of MMTT outcomes to reflect the change of approach for these outcomes

12.3 Changes from Version 1.2 to 1.3

The following changes were made between the SAP versions:

- Change of approach for secondary outcomes from the MMTT to consider analysing as summary measures (peak, AUC) rather than using all individual measurements in the outcomes.
- Change of statistical methods for secondary analysis of MMTT outcomes to reflect the change of approach for these outcomes

12.4 Further changes to the SAP

If there are further revisions to the original proposed analyses, or if any supplementary analyses are planned, these will be documented in a future version of the SAP. The reason for any changes/additions will be documented.

Figure S1. CONSORT Flow Diagram
